4.4.1.2 Statistical Hypothesis, Model, and Method of Analysis

The following null and alternative hypotheses will be evaluated:

- H_0 : There is no difference in the number of bleeding sites from baseline to Week 12 in the Test Product group.
- H_1 : There is a treatment effect on the number of bleeding sites at Week 12, compared to baseline, in the Test Product group.

A Mixed Model for Repeated Measures (MMRM) will be used, with change from baseline in number of bleeding sites as the dependent variable, the categorical time point (Week 3, Week 6, or Week 12), treatment group (Test Product or Reference Product) and time point \times treatment group interaction as fixed effects, and baseline number of bleeding sites as a covariate. Subject will be included as a repeated measure with an unstructured covariance matrix. The Kenward

Roger degrees of freedom approach will be applied. If unstructured covariance matrix does not converge, the following covariance structures will be applied in order until convergence is achieved: 1) Toeplitz, 2) compound symmetry (CS).

Using the above model, the LS mean change from baseline number of bleeding sites will be presented for the Test Product at Week 12, along with 95% CI and p-value, testing for a non-zero change from baseline (Table 14.2.2.1).

The assumption of normality and homogeneity of variance in the MMRM will be investigated. In case of violation of these assumptions, a Wilcoxon Signed Rank Test (within product comparisons with baseline) will be performed to support the MMRM results.

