### 12.3.1 Primary Analysis

A mixed model with repeated measures (MMRM) will be performed on the change from baseline in the number of bleeding sites with product (test or reference), time point (week 3, 6 and 12) and product by time point interaction as fixed effects, and baseline number of bleeding sites as a covariate. Subject will be fitted as a repeated measure with unstructured covariance. Kenward-Roger degrees of freedom will be used.

To test the null hypothesis ( $H_0$ : There is no difference in the number of bleeding sites from baseline to week 12 in the test product group) *vs.* the alternative hypothesis ( $H_1$ : There is a treatment effect on the number of bleeding sites at 12 weeks), estimates of treatment effect at 12 weeks will be based on least squares means (LS means) generated with an appropriate contrast statement. P-values and 95% confidence intervals (CI) will be provided.

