### 12.3.2 Secondary Analysis(es)

Other secondary timepoints (week 3 and 6) related to the number of bleeding sites will be analyzed using the results from the MMRM from the primary analysis. Estimates of treatment effect (changes from baseline at 3, 6 and 12 weeks) and treatment comparisons will be based on least squares means (LS means) generated by appropriate contrast statements. P-values and 95% confidence intervals (CI) will be provided.

The secondary endpoints include (in addition to the number of bleeding sites):

BI (Bleeding Index= Sum of index values over all evaluable tooth sites/Number of evaluable tooth sites). The BI score has a range of 0 to 2; ([see section 9.2.1](#))

Modified Gingival Index (MGI) Assessment= Sum of index values over all evaluable tooth sites/Number of evaluable tooth sites. The MGI score has a range of 0 to 4; ([see section 9.2.2](#))

Overall and interproximal TPI Score = Sum of index values over all evaluable tooth sites/Number of evaluable tooth sites. The TPI score has a range of 0 to 5. ([see section 9.2.4](#))

For the change from baseline for each endpoint above, the same MMRM as applied for the number of bleeding sites will also be applied but including the respective baseline as covariate instead of the baseline number of bleeding sites. Results within and between treatments at each time point will also be obtained and presented in a similar manner.

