Table 5-1	Changes to Protocol Defined Statistical Analysis Plan	31

Abbreviations

Abbreviation	Term
AE	Adverse Event
ANCOVA	Analysis of Covariance
BDRM	Blind Data Review Meeting
BI	Bleeding Index
BOP	Bleeding on Probing
CI	Confidence Interval
COVID-19	Coronavirus Disease of 2019
CRF	Case Report Form
CS	Compound Symmetry
GSK CH	GlaxoSmithKline Consumer Healthcare
ICF	Informed Consent Form
LOCF	Last Observation Carried Forward
LS	Least Square
MedDRA	Medical Dictionary for Regulatory Activities
MFC	Master Formulation Code
MGI	Modified Gingival Index
mITT	Modified Intent-to-Treat
MMRM	Mixed Model for Repeated Measures
OHT	Oral Hard Tissue
OST	Oral Soft Tissue
PP	Per-Protocol
PT	Preferred Term
SAE	Serious Adverse Event
SAP	Statistical Analysis Plan
SD	Standard Deviation
SE	Standard Error
SOC	System Organ Class
TEAE	Treatment Emergent Adverse Event
TPI	Turesky Plaque Index
w/w	Weight for Weight
WHODD	World Health Organization Drug Dictionary

The purpose of this Statistical Analysis Plan (SAP) is to describe the planned analyses and outputs to be included in the Clinical Study Report for Protocol 300029 (Version 3.0, dated 10-May-2023).

1 Summary of Key Protocol Information

This will be a single center, controlled, single blind (examiner blind), randomized, two-treatment arm, parallel study. Study subjects will be over 18 years old, non-smokers, in good general health with clinically measurable levels of gingivitis (defined as those with 10-30% bleeding sites on probing) that meet all study criteria at the Screening and Baseline visits.

Approximately 200 subjects (n=100 per group) will be randomized to ensure 188 evaluable subjects (94 per group) complete the study.

This study will consist of 5 study visits: Screening, Baseline, Week 3, 6 and 12. Gingivitis will be assessed using the Modified Gingival Index (MGI) and the Bleeding Index (BI). Plaque will be assessed by the Turesky modification of the Quigley Hein Index (Turesky Plaque Index [TPI]). All evaluable teeth (in relation to the inclusion/ exclusion general dentition criteria) will be assessed.

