1.4 Sample Size Calculation

A sample size of approximately 100 subjects per treatment group (before presumed 6% dropout rate) is needed to provide at least 90% power to achieve statistical significance (at the 5%, two-sided level) for the primary outcome (change from baseline at 12 weeks in the number of bleeding sites in the sodium bicarbonate group). The assumed treatment efficacy estimates for this calculation comes from the sponsor clinical study (CCI [REDACTED] 2012) report where the change (SD) from baseline at 12 weeks (without pre-prophylaxis) was -14.7 (9.8) bleeding sites.

For the secondary objective (change from baseline at 12 weeks in the number of bleeding sites in the bicarbonate group compared to the negative control group), data from the sponsor clinical study (CCI [REDACTED] 2012) focusing on the non-smoking strata and using a t-test comparing their respective mean changes (SD of change) of 15.5 (10.1) vs. 11.6 (9.1) indicates power will exceed 80%. (PASS 2019 Power Analysis and Sample Size Software (2019). NCSS, LLC. Kaysville, Utah, USA, ncss.com/software/pass). The assumed (from the sponsor clinical study CCI [REDACTED] 2012) +0.7 correlation of the number of bleeding sites at baseline to week 12 helps attain that power.

2 Planned Analyses

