4.4 Analysis of Efficacy

The primary population for assessment of efficacy will be the mITT population. No repeat assessment data is to be used in any efficacy analyses.

Statistical analyses of the endpoints will be performed using the change from baseline, in order to easily present direct estimates for the within-treatment mean changes from baseline (e.g. the primary endpoint).

Descriptive summary statistics will be presented for the actual and change from baseline values at each time point.

All p-values presented will be two-sided and assessed at the 5% significance level. A sequential testing strategy will be used to adjust for multiplicity for the comparison between test and reference products in the number of bleeding sites at Week 12. This will only be assessed for confirmatory evidence if the primary endpoint (change from baseline within the test product at Week 12) achieves a statistically significant reduction. There will be no further adjustments for multiplicity for any other secondary endpoints.

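### The MMRM fits one baseline slope for Weeks 3, 6 and 12; if the true slopes differ, the Week 12 comparison can lose a little precision, and a baseline-by-time point term would prevent this at almost no cost.

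*SAP*

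**What the plan says.** SAP 4.4.1.2 models change from baseline in the number of bleeding sites with time point, treatment and their "interaction as fixed effects, and baseline number of bleeding sites as a covariate". Protocol 12.3.1 matches it: "product by time point interaction as fixed effects, and baseline number of bleeding sites as a covariate". On covariance, the SAP states: "Subject will be included as a repeated measure with an unstructured covariance matrix". Neither document includes a baseline-by-time point term.

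Protocol 12.3.2 carries the model to BI, MGI and TPI, "including the respective baseline as covariate instead of the baseline number of bleeding sites". SAP 4.4.2.2.1, 4.4.2.3.1 and 4.4.2.4.1 do the same, with separate models for overall and interproximal TPI.

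The sample-size text (protocol 12.1, SAP 1.4) assumes a correlation of +0.7 between baseline and Week 12 counts and credits it with supporting the between-arm power. It gives no correlation for Week 3 or Week 6. The LOCF sensitivity analysis (SAP 4.4.3) reuses the same model and so keeps the single slope.

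**The concern.** With change from baseline as the outcome, the slope on baseline at a visit is the baseline correlation times the ratio of that visit's SD to the baseline SD, minus 1. One slope is right only if that product is the same at Weeks 3, 6 and 12. The plan gives no reason to expect this, although it leaves the means and covariance free by visit.

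If the slopes differ, the fitted slope is a weighted compromise and Week 12 is not adjusted with its own slope. Two things follow:

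- The Week 12 test-versus-reference comparison can lose precision. It is the confirmatory test with limited power, and at 94 per arm its power exceeds 80% only with help from the baseline adjustment.
- If dropout also depends on baseline, the within-arm Week 12 LS mean, which is the primary estimate, is moved slightly. Such dropout is missing at random, but the likelihood argument in SAP 4.4.3 also needs the mean model to be right.

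**Working it through.** **Inputs from the documents.** Number completing: "will be randomized to ensure 188 evaluable subjects (94 per group) complete the study". Test-arm change: it "was -14.7 (9.8) bleeding sites". Between-arm mean changes (SD) are 15.5 (10.1) and 11.6 (9.1), with correlation +0.7 at Week 12 (SAP 1.4). Tests: "All p-values presented will be two-sided and assessed at the 5% significance level".

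**Assumed, not in the documents.** Correlations with baseline at Weeks 3 and 6; visit SDs relative to baseline; correlations between Weeks 3-6, 3-12 and 6-12 of 0.80, 0.75 and 0.80; normal data; the dropout pattern.

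**Step 1: the plan's own figures.**
- Primary: expected t = 14.7 / 9.8 × √94 = 14.5, so power is about 100%, consistent with the stated 90% or more.
- Between arms: difference 15.5 − 11.6 = 3.9; pooled SD = √((10.1² + 9.1²)/2) = 9.61. A two-sample t-test (noncentral t) gives 79.0% at 94 per arm and 81.5% at 100.
- With adjustment at r = 0.7 and equal SDs: baseline SD = 9.61/√(2 − 2×0.7) = 12.41; residual SD = 12.41 × √(1 − 0.49) = 8.86; power 85.1% at 94 per arm (85.5% by normal approximation). The stated power above 80% is reproduced.

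**Step 2: cost of a common slope.** Let β_t = r_t × SD_t/SD_0 − 1, and let Σ be the residual covariance under visit-specific slopes. In large samples the common slope is c = (1ᵀΣ⁻¹β)/(1ᵀΣ⁻¹1). The Week 12 variance is multiplied by 1 + SD_0² (β_12 − c)² / σ²_12, where σ_12 is the Week 12 residual SD.

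| Baseline correlation, Weeks 3/6/12 | Slopes | c | Residual SD | Variance | Power |
|---|---|---|---|---|---|
| 0.70/0.70/0.70 | −0.30, −0.30, −0.30 | −0.300 | 8.86 → 8.86 | +0% | 85.1 → 85.1% |
| 0.80/0.75/0.70 | −0.20, −0.25, −0.30 | −0.235 | 8.86 → 8.90 | +0.8% | 85.1 → 84.8% |
| 0.90/0.80/0.70 | −0.10, −0.20, −0.30 | −0.130 | 8.86 → 9.11 | +5.6% | 85.1 → 83.1% |
| 0.85/0.78/0.70, visit SDs 1/0.9/0.8 of baseline | −0.15, −0.30, −0.44 | −0.268 | 7.62 → 7.95 | +9.1% | 93.7 → 91.7% |

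Third row: 1 + (12.41 × 0.170 / 8.86)² = 1.057 (1.056 before rounding). Other between-visit correlations in the range 0.75-0.88 take that row to about 7% (power 82.7%) and put the last row at 8-9%. The last row starts from higher power because shrinking SDs reduce the residual SD.

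**Step 3: how far power could fall.** At 94 per arm, power reaches 80% when the residual SD is 9.54 (normal approximation). That needs a slope error of √(9.54² − 8.86²)/12.41 = 0.285 against a true slope of −0.30, which is almost no baseline adjustment.

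**Step 4: effect of the eligibility window.** Inclusion requires BOP between 10% and 30%. With six sites on each of 20 to 28 teeth (120 to 168 sites), that is about 12 to 50 bleeding sites. If BOP is uniform over the window, the baseline SD is 0.20 × sites/√12, or 6.9 to 9.7, and about 8.9 when tooth counts are equally mixed. Holding the slopes and residual SDs fixed, an SD of 8.9 cuts the inflation in rows 2 to 4 to 0.4%, 2.9% and 4.1%.

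**Step 5: LS-mean shift.** To first order, the shift is (β_12 − c) × (mean baseline of those still observed − mean baseline of all). Large-sample fits with 6% dropout and an odds ratio of 3 per baseline SD gave test-arm Week 12 shifts of 0.00, 0.06, 0.12 and 0.15 sites for the four rows. The LS-mean SE is about 0.8-0.9. At 15% dropout the non-zero shifts were 0.14-0.36. The arm difference moved by 0.01 or less when dropout acted alike in both arms, and by 0.06-0.16 of 3.9 sites when it depended on baseline in the test arm only.

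**Step 6: finite-sample check.** This used 400 simulated trials of 100 per arm with 6% baseline-dependent dropout, fitted by maximum likelihood rather than REML with Kenward-Roger. The single slope raised the empirical SE of the difference by 0.2% to 6%. Power was 85.0 against 85.3%, 84.5 against 85.5%, 83.8 against 86.8% and 92.0 against 95.3%. With baseline-dependent dropout in the test arm only, the loss was 1-5 points. Each power carries about ±2 points of simulation error. The primary within-arm |t| never fell below 12.

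**The case against.** The strongest reply is that the premise is not in the documents. They give one correlation, at Week 12, and nothing that shows decay. Correlation is also not slope: a falling correlation with a rising SD can leave the slopes equal. This stands. The loss is conditional, and its size rests on assumed Week 3 and Week 6 values.

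The BOP window probably narrows the baseline SD and could roughly halve the effect. That also stands, although the actual baseline SD is unknown.

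The protocol and SAP agree with each other. With complete data, randomisation keeps the Week 12 between-arm contrast unbiased under a common slope. No type I error problem or contradiction is shown, so this is a choice of model and not a mistake.

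A reader might infer that the plan certainly loses precision, or that the primary estimate is biased enough to matter. The documents support neither. Equal slopes give no loss and no shift. The LS-mean shift needs unequal slopes and baseline-dependent dropout together, and protocol 12.3.4 reports only one subject lost in the earlier 12-week study. Much larger losses can be produced by assuming a Week 12 correlation well below 0.7, but that departs from the plan's own figure.

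None of these points shows a disadvantage in adding the term. With equal slopes, the interaction model matched the single-slope model in the simulation (mean SE 1.280 for both).

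**Conclusion.** The point holds as a conditional, low-priority improvement. Keeping the plan's +0.7 at Week 12 and assuming correlations of 0.80-0.90 at Week 3 and 0.75-0.80 at Week 6 with constant SDs, the single slope inflates the Week 12 between-arm variance by about 1-7%. That costs up to about 2.5 power points from about 85%. The loss is nil with equal slopes and smaller if the BOP window narrows the baseline SD. If visit SDs also shrink, the inflation can reach 8-9%, but power then stays near 92%. The 5-point loss in the simulation needs dropout that depends on baseline in the test arm only.

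The test-arm LS mean could shift by 0 to 0.15 sites at about 6% baseline-dependent dropout. That is at most about 1% of the assumed 14.7-site change (0.15/14.7) and less than a fifth of its SE, so the primary conclusion is not at risk.

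**What to change.** Before unblinding, add baseline-by-time point as a fixed effect to the MMRM in SAP 4.4.1.2, and to the corresponding models for BI, MGI, overall TPI and interproximal TPI, each with its own baseline. The LOCF and per-protocol runs then inherit it. Record the change in SAP Table 5-1 as a departure from protocol 12.3.1 and 12.3.2.

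State that within-arm LS means are evaluated at the overall mean baseline, with one value for both arms and all visits. This matters only for the within-arm estimates. Without a baseline-by-treatment term, the between-arm contrast is the same at any baseline value.

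The cost is two extra parameters per model and a few lines of SAP text, with no added data, visits or subjects. After unblinding, the same change would be a post hoc choice of model.

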4.4.2.2.1 Statistical Hypothesis, Model and Method of Analysis

For comparisons to baseline within each treatment group, the following null and alternative hypotheses will be evaluated for post-baseline time points at Week 3, Week 6 and Week 12, respectively:

- H_0 : There is no difference in the BI score from baseline.
- H_1 : There is a treatment effect on the BI score compared to baseline.

For comparisons to negative control, the following null and alternative hypotheses will be evaluated for post-baseline time points at Week 3, Week 6, and Week 12, respectively:

- H_0 : There is no difference in change from baseline in the BI score in the Test Product group compared to the Reference Product group.
- H_1 : There is a difference in change from baseline in the BI score in the Test Product group compared to the Reference Product group.

A MMRM will be used as described in [Section 4.4.1.2](#), with change from baseline in BI score as the dependent variable and baseline BI score as a covariate instead of baseline number of bleeding sites.

Using the above model, the LS mean change from baseline BI score will be presented for each study product at each post-baseline time point with corresponding 95% CIs and p-values to test for a non-zero change from baseline.

The difference in LS mean change from baseline BI score (Test Product – Reference Product) will also be presented at each post-baseline time point with corresponding 95% CIs and p-values to test for a non-zero difference (Table 14.2.3.2.1).

The assumption of normality and homogeneity of variance in the MMRM will be investigated. In case of violation of these assumptions, a Wilcoxon Rank Sum test (between products comparisons) and Wilcoxon Signed Rank Test (within product comparisons with baseline) will be performed to support the MMRM results.

The MMRM model will be repeated using the LOCF approach for the mITT population (Table 14.2.3.2.2).

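### The covariance fallback forces one residual variance on Weeks 3, 6 and 12, so if it is ever used the Week 12 standard error can be wrong in either direction

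*SAP*

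**What the plan says.** SAP 4.4.1.2 models change from baseline at Weeks 3, 6 and 12, with baseline as covariate, an unstructured within-subject covariance matrix and Kenward-Roger degrees of freedom. On non-convergence, "the following covariance structures will be applied in order until convergence is achieved: 1) Toeplitz, 2) compound symmetry (CS". It names no heterogeneous version of either structure and no robust standard error.

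The same section says that normality and homogeneity of variance will be examined. A violation adds a supportive Wilcoxon test; it does not alter the covariance structure or the MMRM standard errors.

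The rule reaches beyond the primary endpoint. SAP 4.4.2.1.1 takes the between-product comparison of bleeding sites from the same model. For the Bleeding Index, SAP 4.4.2.2.1 says "A MMRM will be used as described in" Section 4.4.1.2, and the MGI and TPI sections do likewise. The LOCF and per-protocol fits also reuse it.

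On error rate, SAP 4.4 states: "All p-values presented will be two-sided and assessed at the 5% significance level". The Week 12 between-product test on bleeding sites is confirmatory if the primary within-arm test succeeds.

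Protocol 12.3.1 specifies unstructured covariance with no fallback, and SAP Table 5-1 does not list the fallback as a change.

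**The concern.** Plain Toeplitz has one variance and two lag covariances; plain compound symmetry has one variance and one covariance. Under either, the Week 12 variance is replaced by roughly the average over the three visits. Kenward-Roger adjusts for small samples within the assumed structure and does not repair a wrong one.

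If variability of change grows over follow-up, the Week 12 standard error is pulled down and the test is too liberal. If it shrinks, the standard error is pushed up and power is lost. What is at stake is the only randomised comparison with confirmatory status, and the intervals for the other secondary endpoints. A prespecified fallback exists for the rare case in which it is needed, and it should be sound there. This one gives up visit-specific variances at its first step, although intermediate structures would keep them.

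**Working it through.** **Inputs from SAP 1.4**

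- Primary: "is needed to provide at least 90% power to achieve statistical significance (at the 5%, two-sided level) for the primary outcome", with an assumed change that "without pre-prophylaxis) was -14.7 (9.8) bleeding sites".
- Between arms: "mean changes (SD of change) of 15.5 (10.1) vs. 11.6 (9.1) indicates power will exceed 80" per cent.
- Baseline: "0.7 correlation of the number of bleeding sites at baseline to week 12 helps attain that power".
- Attrition: 100 per arm "before presumed 6% dropout rate", so 100 × 0.94 = 94 per arm.

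**Assumed, because the documents do not give them:** the Week 3 and Week 6 residual SDs relative to Week 12, and the between-visit residual correlations (0.80 for Weeks 3–6, 0.64 for Weeks 6–12, 0.51 for Weeks 3–12).

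**1. The plan's own figures**

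- Primary: effect size 14.7/9.8 = 1.5. Power at n = 94 is about 100%; 7 subjects would give 90%.
- Between arms: difference 15.5 − 11.6 = 3.9; pooled SD √((10.1² + 9.1²)/2) = 9.61. Unadjusted power is about 79% at 94 per arm and 82% at 100.
- With r = 0.7 and equal variances at baseline and Week 12, baseline adjustment multiplies the variance of change by (1 − 0.7²)/(2(1 − 0.7)) = 0.51/0.60 = 0.85. The residual SD is 9.61 × √0.85 = 8.86, and power is about 85% at 94 and 87% at 100.

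The stated figures therefore reproduce. With 100 per arm randomised, 6% dropout and a correct covariance matrix, the Week 12 between-arm SE is about 1.28 and power is Φ(3.9/1.28 − 1.96) ≈ 86%.

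**2. Hand approximation to the fallback**

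With complete data, the ratio of model-based to true Week 12 SE is about q = √((a² + b² + 1)/3), where a:b:1 are the Week 3:6:12 residual SD ratios. Two-sided size is 2(1 − Φ(1.96q)).

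- 0.8:0.9:1 gives q = √(2.45/3) = 0.904, size 7.7%.
- 1.2:1.1:1 gives q = √(3.65/3) = 1.103, size 3.1%.

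**3. Best-fitting Toeplitz and compound symmetry (minimum Kullback-Leibler) at 6% dropout**

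| SD ratio, Weeks 3:6:12 | Model SE / true SE | Two-sided size |
|---|---|---|
| 0.7:0.85:1 | 0.851–0.855 | 9.4–9.5% |
| 0.8:0.9:1 | 0.897–0.900 | 7.8–7.9% |
| 0.9:0.95:1 | 0.945–0.948 | 6.3–6.4% |
| 1:1:1 | 0.995–0.998 | 5.0–5.1% |
| 1.1:1.05:1 | 1.046–1.050 | 4.0% |
| 1.2:1.1:1 | 1.10 | 3.0–3.1% |

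In the last row the model SE is about 1.41 against a true 1.28. Power is Φ((3.9 − 1.96 × 1.41)/1.28) ≈ 81%, down from 86%.

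**4. Simulation check** (REML, 500 trials in each of three scenarios, 100 per arm, 6% dropout)

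- 0.8:0.9:1: mean SE 1.15 under either fallback against 1.28 unstructured; rejection under the null 6.8–7.4% against 4.8%.
- 1.2:1.1:1: mean SE 1.41–1.42 against 1.28; rejection 2.6–2.8% against 4.6%.
- The unstructured model converged in all 1,500 trials.

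**5. Unequal spacing alone** (equal variances, 3-week and 6-week gaps)

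The Week 12 SE changes by 0% with complete data, at most 0.6% at 6% dropout and at most 1.7% at 15% dropout.

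**6. Primary test**

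The statistic is about 1.5 × √94 = 14.5. With an SE 10% too large it would be 14.5/1.10 = 13.2.

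**The case against.** The strongest reply is that the branch is close to hypothetical. An unstructured 3x3 matrix has six parameters, about 188 subjects are expected to complete, and SAP 4.4.3 expects little missing data. Every simulated trial converged. This stands, and it is why the point is minor.

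The SAP also has partial safeguards: variance homogeneity is examined, rank tests may be added, and SDs are tabulated at every visit, so a mismatch would be visible. That is fair, but the Wilcoxon results only support the MMRM, whose interval and p-value would stay as they are.

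Two stronger readings are tempting, and the documents do not support them.

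- A reader might infer that the fallback inflates the type I error. That needs the SD to rise over time, and no Week 3 or Week 6 SD is given. A falling SD makes the test conservative.
- A reader might infer that the unequal visit gaps, which neither fallback reflects, are themselves a source of error. Step 5 shows that they barely move the Week 12 standard error at the planned dropout.

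**Conclusion.** The point holds as a conditional, low-severity weakness. If the unstructured model fails and residual variances differ by visit, the prescribed fallback misstates the Week 12 standard error: about 10% too small under 0.8:0.9:1, about 10% too large under 1.2:1.1:1, and essentially correct with equal SDs. The sizes rest on assumed SD ratios and correlations, because the documents give SDs of change for Week 12 only (9.8 for the primary calculation; 10.1 and 9.1 by arm). The direction cannot be settled from them.

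A reader might also infer that the primary result is at risk. It is not: a within-arm effect of 1.5 SD leaves the conclusion unchanged under any scenario examined, although its confidence interval would be affected. The exposure is the gated Week 12 between-arm test, where planned power is about 86%, and the secondary intervals.

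**What to change.** Replace the fallback list in SAP 4.4.1.2 with:

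1. the same unstructured model, refitted with a Cholesky parameterisation (SAS TYPE=FA0(3)) or with supplied starting values;
2. heterogeneous Toeplitz;
3. heterogeneous compound symmetry.

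Keep Kenward-Roger degrees of freedom throughout, as the protocol and SAP already specify. The first step changes only the computation, not the model; the other two keep a separate variance for each visit. The secondary endpoints inherit the change by cross-reference. The cost is one SAP sentence before unblinding, and nothing changes if the unstructured model converges.

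### The primary within-arm Week 12 CI and p-value leave out the sampling error of the mean baseline, so for the population mean change the interval is slightly too narrow unless the slope of Week 12 on baseline is near 1

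*SAP*

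**What the plan says.** The primary endpoint is a single-arm quantity, the Week 12 change in the number of bleeding sites in the Test arm (SAP 4.4.1.1). The null hypothesis in SAP 4.4.1.2 is "There is no difference in the number of bleeding sites from baseline to Week 12 in the Test Product group".

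Both arms enter one MMRM on change from baseline, with visit, treatment, their interaction and "baseline number of bleeding sites as a covariate". Covariance is unstructured and degrees of freedom are Kenward-Roger. From this model, "the LS mean change from baseline number of bleeding sites will be presented for the Test Product at Week 12, along with 95% CI", with a p-value for a non-zero change. Protocol 12.3.1 agrees: "estimates of treatment effect at 12 weeks will be based on least squares means (LS means) generated with an appropriate contrast statement". SAP 4.4 adds: "All p-values presented will be two-sided and assessed at the 5% significance level".

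Neither document states the baseline value at which the LS mean is evaluated, or says that the interval is conditional on the observed baselines. Neither adds a term for the sampling error of the mean baseline.

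**The concern.** An LS mean from a model with a baseline covariate is a prediction at a fixed baseline value, usually the mean of all subjects in the model. Its standard error treats that value as known. The null hypothesis, however, concerns the mean change in a population, and the mean baseline of 188 subjects is itself a sample quantity. The missing variance is the squared slope of change on baseline times the variance of the mean baseline. Kenward-Roger does not restore it, because baseline remains a fixed regressor.

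In the Test-Reference difference the pooled baseline mean cancels and nothing is lost. In one arm's mean change it does not cancel, and here that is the primary result. The same construction serves every within-arm contrast: five outcomes (bleeding sites, BI, MGI, overall and interproximal TPI) × two arms × three visits = 30, including the primary one. What is at stake is the accuracy of the reported precision.

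**Working it through.** **Inputs.** From SAP 1.4: the primary planning change "was -14.7 (9.8) bleeding sites", an assumed +"0.7 correlation of the number of bleeding sites at baseline to week 12 helps attain that power", and, for the between-arm comparison, "mean changes (SD of change) of 15.5 (10.1) vs. 11.6 (9.1) indicates power will exceed 80"%. Evaluable n is 94 per arm (SAP 1), and 94/(1 − 0.06) = 100 randomized. The level is 5% two-sided (SAP 4.4). The baseline SD and the Week 12 SD are not given.

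**The plan's own figures.** Primary: 14.7/(9.8/√94) = 14.5, so power exceeds 99.9%, consistent with the stated 90% or more. Secondary: pooled SD √((10.1² + 9.1²)/2) = 9.61, and a t-test on a difference of 15.5 − 11.6 = 3.9 has power 79.4% at 94 per arm and 81.8% at 100. Covariate adjustment with r = 0.7 and equal SDs gives 85.5% at 94. The plan's power statements therefore reproduce. It gives no coverage figure beyond the nominal 95%.

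**Formulas.** Let sX and sY be the baseline and Week 12 SDs, k = sY/sX and b = r·k the slope of Week 12 on baseline. The slope of change on baseline is b − 1.

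- Model variance of the LS mean: sY²(1 − r²)/n.
- Variance for the population mean change, with the LS mean at the pooled baseline mean: add (b − 1)²·sX²/(2n).
- Coverage = 2Φ(1.96 × SE ratio) − 1.
- Baseline SD implied by the planning figures: sX = 9.8/√(1 + k² − 2rk).

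**Equal SDs (k = 1, assumed).** sX = 9.8/√0.6 = 12.65.

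- Model SE = 12.65 × √0.51/√94 = 0.932, half-width 1.83 sites.
- Added variance = 0.3² × 12.65²/188 = 0.077, so SE = √(0.868 + 0.077) = 0.972, half-width 1.91 sites.
- SE ratio = √(0.51/0.555) = 0.959, coverage 94.0%, test level 6.0%.
- The test statistic for −14.7 is 15.8 with the model SE and 15.1 with the full SE.

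If the LS mean were evaluated at the Test arm's own baseline mean, coverage would be 92.9% and the level 7.1%.

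**Range over the unknown SD ratio (r = 0.7).**

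| Week 12 SD / baseline SD | Slope b | Implied baseline SD | SE ratio | Coverage |
|---|---|---|---|---|
| 0.7 | 0.49 | 13.7 | 0.811 | 88.8% |
| 0.8 | 0.56 | 13.6 | 0.878 | 91.5% |
| 0.9 | 0.63 | 13.2 | 0.926 | 93.1% |
| 1.0 | 0.70 | 12.65 | 0.959 | 94.0% |
| 1.1 | 0.77 | 12.0 | 0.979 | 94.5% |
| 1.2 | 0.84 | 11.2 | 0.991 | 94.8% |
| 1.43 | 1.00 | 9.6 | 1.000 | 95.0% |

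**Simulation.** The SAP's MMRM was simulated with three visits, unstructured covariance, a common baseline slope, complete data, 94 per arm and 20,000 runs, using t with 2n − 3 degrees of freedom in place of Kenward-Roger. Coverage was 94.2% at ratio 1.0, 91.5% at 0.8 and 89.0% at 0.7. Adding the missing term brought it to 94.8–95.2%.

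**Effect of the entry window.** Entry requires bleeding at 10–30% of sites (Protocol 5.2). On 168 sites (SAP 4.4.1.1) that is about 17 to 50. With baseline cut to mimic this window and pre-selection SD ratios of 0.8 and 1.0, simulated coverage was 93.7% to 94.6%.

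**The case against.** The strongest reply is that the interval is exact for a narrower target, the mean change given the baselines observed, and that such LS means are routine MMRM output. That is true, but the SAP does not state that target, and its null hypothesis reads as one about the population.

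Second, the entry window argues against the lower rows of the table. A uniform spread over 17 to 50 sites has SD 33.6/√12 = 9.7. With r = 0.7 and SD of change 9.8, that requires a Week 12 SD of about 13.7 and a slope of 0.7 × 13.7/9.7 = 0.99, at which almost nothing is lost. A baseline SD of 13.7 in a window of half-width 16.8 would need subjects concentrated at both ends. This stands as a reason to expect a small shortfall. It does not prove that there is none: the uniform spread is an assumption, and so is carrying the 2012 study's correlation over to a restricted baseline.

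Third, Table 14.2.2.1.1 already reports the raw SE of change, from which a reader could form a paired interval (9.8/√94 = 1.01 at the planning SD). A signed rank test is also planned if model assumptions fail. Both are useful, but neither replaces the primary CI and p-value.

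A reader might infer that the correlation of 0.7 by itself gives 94% and 6%. It does not: equal SDs and an LS mean at the pooled baseline mean are also needed, and the documents give neither. A reader might also take about 90% or less as the expected coverage, because a falling count may lose spread. The documents do not support picking out that end of the range, since ratios above 1 bring coverage back to 94.5–95%.

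**Conclusion.** The point holds as a small matter of CI accuracy. As an interval for the population mean change, the primary within-arm CI is slightly too narrow unless the slope of Week 12 on baseline is near 1. Coverage is about 94% and the test level about 6% if r = 0.7, the two SDs are equal and the LS mean is taken at the pooled baseline mean. Over SD ratios from 0.7 to 1.43, coverage runs from about 89% to 95%. With baseline restricted to the entry window it is about 94–94.6% in most of the cases simulated.

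It would be wrong to infer that the trial could succeed on its primary endpoint because of this. At the planned effect the test statistic is about 15 with either SE, so neither the primary decision nor the gate to the between-arm test changes. The Test-Reference difference is unaffected in any case. The planning data give no effect sizes for BI, MGI or TPI, so the same margin cannot be shown for their within-arm contrasts.

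**What to change.** Take the within-arm changes and their CIs from a constrained longitudinal model: baseline and Weeks 3, 6 and 12 in the response vector, a baseline mean common to both arms, and unstructured covariance. Take the between-arm difference from the same fit, so that the reported arm changes subtract to the reported difference.

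Alternatively, keep the present MMRM and add slope² × Var(mean baseline) to the variance of each within-arm LS mean, where the slope is that of change on baseline. In that case, state that the LS mean is evaluated at the pooled baseline mean.

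The cost is a SAP wording change and one changed or extra model fit. In the equal-SD case the within-arm CI becomes about 4% wider (0.972/0.932 = 1.04; half-width 1.83 to 1.91 sites).
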